6.4.3 Analysis of Relapse

Definition of Relapse

In Study 109MS303, relapses are defined as new or recurrent neurologic symptoms not associated with fever or infection, lasting at least 24 hours, and accompanied by new objective neurological findings upon examination by the *treating (or examining) neurologist*. The subject must have objective signs on the *treating (or examining) neurologist's* examination confirming the event (i.e., an objective or protocol-defined relapse). New or recurrent neurologic symptoms that evolve gradually over several weeks to months are not to be considered an acute relapse. New or recurrent neurologic symptoms that occur less than 30 days following the onset of a protocol-defined relapse should be considered part of the same relapse. i.e., if 2 relapses have onset days that are ≤29 days of one another, they will be counted only as 1 relapse, and the onset date used in the analysis will be the onset date of the first relapse.

In Studies 109MS301 and 109MS302, relapses are defined as new or recurrent neurologic symptoms not associated with fever or infection, lasting at least 24 hours, and accompanied by new objective neurological findings upon examination by the *examining neurologist*. The subject must have objective signs on the *examining neurologist*'s examination confirming the event (i.e., an objective or protocol-defined relapse), and additionally must then be reviewed and confirmed by the *Independent Neurology Evaluation Committee (INEC)* (INEC-confirmed relapses). New or recurrent neurologic symptoms that evolve gradually over several weeks to months were not to be considered an acute relapse. New or recurrent neurologic symptoms that occur less than 30 days following the onset of an INEC confirmed relapse should be considered part of the same relapse. i.e., if 2 relapses have onset days that are ≤29 days of one another, they will be counted only as 1 relapse, and the onset date used in the analysis will be the onset date of the first relapse.

Therefore, Studies 109MS301, 109MS302, and 109MS303 all utilize essentially the same definition for objective (i.e., protocol-defined) relapses, given that there is no Independent Neurology Evaluation Committee (INEC) in Study 109MS303. Therefore, analyses of relapse for the final analysis of Study 109MS303 will be based primarily on objective (i.e., protocol-defined) relapses.

Annualized Relapse Rate

Annualized relapse rate (ARR) will be summarized using the following analysis populations, treatment grouping, and datasets:

- Studies 109MS301/302/303 ARR, overall and over time, using the Study 303 ITT Population with Combined Treatment Grouping and Combined Data; and
- Study 109MS303 ARR using the Study 303 ITT Population with Combined Treatment Grouping and Study 109MS303 data only.

The number of subjects with a given number of relapses (categories of 0, 1, 2, 3, and 4 or more relapses), total number of relapses, and total number of subject-years of follow-up will be summarized by treatment group. The unadjusted ARR will be calculated for each treatment group as the total number of relapses divided by the total number of subject-years

of follow-up. Relapses and follow-up time that occur after first use of alternative MS medications are excluded from the calculations.

The adjusted ARR and associated 95% confidence interval will be calculated for each treatment group by using a negative binomial regression model for unadjusted ARR, adjusting for baseline EDSS score (≤2.0 vs. >2.0), baseline age (<40 vs. ≥40 years old), region, and baseline relapse rate (i.e., the number of relapses in the year prior to the date of first dose in the previous study) as covariates. The baseline definition for these covariates will be based on Previous Study Baseline.

The logarithmic transformation of the time on the study will be included in the model as the "offset" parameter. If the data are underdispersed, or if the negative binomial regression model does not converge, a Poisson regression model with the same covariates will be used instead of the negative binomial regression model. Dispersion will be evaluated from the Pearson Chi-Square statistic. If the ratio of the Pearson Chi-Square statistic to the degrees of freedom is ≤ 1 which indicates no overdispersion, then a Poisson regression model with adjustment for underdispersion will be used.

In addition, the subject relapse rate will be calculated as the number of relapses for an individual subject divided by follow-up time in years for that subject excluding follow-up time after first use of alternative MS medication. Subject relapse rate will be summarized descriptively by treatment group.

ARR analyses over time will be presented by various time intervals in order to elucidate onset and maintenance of effect over time. For example, time intervals one year in length may be considered.

For ARR analyses, data following first use of alternative MS medications in the given dataset used for analysis will be excluded. If a subject did not experience a relapse prior to first starting an alternative MS medication, the subject's follow-up time will be censored at the time the first alternative MS medication is started. Likewise, if a subject did not experience a relapse prior to study withdrawal, the subject's follow-up time will be censored on the last date followed. The start date for calculation of ARR will be date of first dose, and if date of first dose is incomplete, date of randomization or enrollment will be used.

Proportion of Subjects Who Relapsed

The proportion of subjects who relapsed will be summarized using the following analysis populations, treatment grouping, and datasets:

• Studies 109MS301/302/303 proportion relapsed using Study 303 ITT Population with Combined Treatment Grouping and Combined Data.

The proportion of subjects relapsed can be estimated as the probability of relapses from the Kaplan-Meier curve of the time to the first relapse (i.e., Kaplan-Meier product-limit estimator). If there are no early withdrawals, the Kaplan-Meier estimate of the proportion of subjects relapsed is the same as the observed proportion of subjects relapsed. If there are early withdrawals, the Kaplan-Meier estimate has the advantage of taking into account the length of follow-up for the early withdrawals, without making any assumptions about whether those subjects relapsed or not.

Proportion relapsed analyses over time will be presented based on Kaplan-Meier curves. The estimated proportion of subjects relapsed at key timepoints from the Kaplan-Meier curves will be presented.

For proportion relapsed analyses, data following first use of alternative MS medications will be excluded. If a subject did not experience a relapse prior to first starting an alternative MS medication, the subject will be censored at the time the first alternative MS medication is started. Likewise, if a subject did not experience a relapse prior to study withdrawal, the subject will be censored on the last date followed. The start date for calculation of time to relapse will be date of first dose, and if date of first dose is incomplete, date of randomization will be used.

6.4.4 Analysis of Progression

Definition of Progression

In Study 109MS303, sustained disability progression will be assessed from the EDSS scores performed as per the protocol defined schedule of assessments at regular visits relative to the baseline EDSS score in the extension study, and well as from the baseline scores in previous study. Sustained disability progression is defined as at least a 1.0 point increase on the EDSS from a baseline EDSS ≥1.0 that is sustained for at least 24 weeks or a 1.5 point increase on the EDSS progression is defined as sustained (or confirmed) when this minimum EDSS change is present on the next study visit occurring after 154 days or longer from the initial observation. The 154 day interval is based on the visit windows allowed in the protocol around the target visit day

The date of the initial visit at which the minimum increase in the EDSS is met will be the date of onset of the progression (tentative progression).

Progression will not be confirmed at a visit where a relapse is also occurring. A subject is considered to be having a relapse for at least 29 days after the start date of an objective relapse. If a subject meets the defined EDSS criteria of sustained progression and is also having a relapse, the subject will be required to meet the defined minimum EDSS criteria at the subsequent visit.

Disability progression can be confirmed at the early (premature) study withdrawal visit, according to the rules above, as long as the early withdrawal visit is not also a relapse assessment visit.

Death due to MS will be counted as progression. If the subject was in the midst of a tentative progression at the time of death (e.g. the EDSS evaluation prior to death is a tentative progression), the progression date will be the date of the start of the progression. If the subject had a confirmed EDSS progression prior to death, the progression date is the start date of the tentative progression. Otherwise, the progression date will be the date of death.

In Studies 109MS301 and 109MS302, the same definition of sustained disability progression will be used as in Study 109MS303 (i.e., requiring a 24 week confirmation).

Sustained disability progression will be summarized using the following analysis populations, treatment groupings, and datasets:

- Studies 109MS301/302/303 time to sustained (24 week) disability progression using the Study 303 ITT Population with Combined Treatment Grouping and Combined Data with previous study baseline; and
- Studies 109MS301/302/303 time to sustained (24 week) disability progression using the Study 303 ITT Population with Combined Treatment Grouping and Study 109MS303 data only with 109MS303 baseline.

Time to sustained disability progression will be presented based on Kaplan-Meier curves. The estimated proportion of subjects with sustained disability progression at key timepoints based on the Kaplan-Meier curve will be presented.

For these sustained disability progression analyses, subjects who do not have a sustained progression based on the above definition will be censored. The censor date will be the date of the last EDSS assessment, or the last EDSS assessment prior to first use of an alternative MS medication, unless the subject has a tentative progression at this assessment. For subjects with a tentative progression at this assessment, (or at the last EDSS assessment prior to first use of alternative MS medication that was subsequently not confirmed) the censor date will be the date of the EDSS assessment prior to the last EDSS assessment. Subjects who withdraw from the study after the baseline visit but prior to the first scheduled EDSS assessment will be censored at baseline. The start date for calculation of time to progression will be date of first dose, and if date of first dose is incomplete, date of randomization will be used.

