## **8. STUDY POPULATION**

### **8.1. Inclusion Criteria**

To be eligible to participate in this study, candidates must meet the following eligibility criteria at the time of the Baseline Visit:

1. Ability to understand the purpose and risks of the study and provide signed and dated informed consent and authorization to use protected health information (PHI) in accordance with national and local subject privacy regulations.
2. Subjects who participated in and completed as per protocol previous BG00012 clinical studies 109MS301 or 109MS302, including those subjects who received an open-label, approved MS therapy, and completed the modified visit schedule.
3. All male subjects and female subjects of childbearing potential must practice effective contraception during the study and be willing and able to continue contraception for 30 days after their last dose of BG00012. For further details of contraceptive requirements for this study, please refer to Section 15.5.3.

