## 11.6. Concomitant Therapy and Procedures

A concomitant therapy is any drug or substance administered from the time of the subject's written consent until the subject's End of Study Visit.

A concomitant procedure is any therapeutic intervention (e.g., surgery/biopsy, physical therapy) or diagnostic assessment (e.g., blood gas measurement, bacterial cultures) performed from the time the subject is enrolled in the study until the subject's End of Study Visit, unless the subject is being followed for study-related toxicity.

Concomitant treatment with any of the following is *not* allowed unless otherwise described in this protocol:

- Any alternative drug treatments directed toward the treatment of MS, such as chronic immunosuppressant therapy or other immunomodulatory treatments (including, but not limited to, IFN-beta, IFN-alpha, GA, natalizumab, fingolimod, teriflunomide, cyclophosphamide, methotrexate, azathioprine, 4-aminopyridine or related products, etc.), with the exception of acute management of protocol-defined relapse (as

CONFIDENTIAL

The information contained herein may not be used, disclosed, or published without the written consent of Biogen MA Inc.

described below) and subjects with prolonged lymphopenia (as described in Section 11.3).

- Any investigational product, including investigational symptomatic therapies for MS and investigational therapies for non-MS indications.
- Any systemic steroid therapy including, but not limited to, oral corticosteroids (e.g., prednisone) or periodic (e.g., monthly) treatment with intravenous methylprednisolone (IVMP), except for protocol-defined treatment of relapses as described below. Steroids that are administered by non-systemic routes (e.g., topical, inhaled) or systemic steroid therapy for limited, short-term treatment of general medical conditions are allowed.
- Total lymphoid irradiation, cladribine, T-cell or T-cell receptor vaccination, any therapeutic monoclonal antibody, mitoxantrone, cyclosporine, intravenous immunoglobulin, plasmapheresis, or cytapheresis.

Subjects who receive any of these restricted medications will be required to discontinue permanently BG00012 and will be withdrawn from the study unless otherwise described in this protocol as outlined in Section 11.2.

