**14.3.3.2. Visits 18, 22, 26, 30, and 34 (Weeks 168, 216, 264, 312, and 360 ±7 Days)**

Treating Neurologist

- Physical examination
- EDSS (may be performed by the *examining neurologist*)
- Monitoring of AEs

Treating Nurse

- Vital signs
- Collection of blood for hematology and lymphocyte analysis
- Collection of blood for blood chemistry
- Collection of urine for urine pregnancy test in women of childbearing potential; results must be known prior to BG00012 distribution
- Collection of urine for urinalysis. If urinalysis is abnormal, see Section 11.2.
- BG00012 distribution
- Recording concomitant medication and AEs

Examining Technician (if designated by *treating neurologist*)

- Visual function test

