2.2 Overall Study Duration and Follow-Up

Eligible subjects were enrolled at Week 96 (Visit 24) of their previous BG00012 study (109MS301 or 109MS302), which would serve as the Baseline Visit for this extension study. If the Baseline Visit could not be combined with Visit 24 of their previous BG00012 study, the subjects may have been randomized within 6 months of Visit 24, provided that they still were eligible for enrollment. The Baseline visit assessments may have been repeated if there was a gap in study treatment.

Subjects reported to the study site every 4 weeks for the first 24 weeks (Visit 1 through Visit 6) and every 12 weeks thereafter for up to 8 years.

Subjects who completed the Week 384 visit (Visit 36), regardless of further need to monitor lymphocytes on study, completed an End of Study Visit at Week 388 ± 7 days. For subjects who have completed Visit 36, an End of Study Visit was completed 4 weeks after their next visit (scheduled or unscheduled), regardless of further need to monitor lymphocytes on study. Subjects who permanently discontinued BG00012 prior to Week 384, regardless of further need to monitor lymphocytes on study, completed a Premature Study Treatment Withdrawal Visit within 4 weeks after their last dose of BG00012. Subjects who completed BG00012 treatment or permanently discontinued BG00012 for any reason and who had a lymphocyte count <LLN were not withdrawn from the study. These subjects were followed according to Protocol Section 11.3.

For subjects who have already completed Visit 36 (or beyond) prior to the Protocol Version 8, an End of Study Visit was completed 4 weeks after their next visit (scheduled or unscheduled), regardless of further need to monitor lymphocytes on study. For subjects who have not completed Visit 36 prior to Protocol Version 8, Visit 36 served as the last scheduled Visit and an End of Study Visit was completed 4 weeks after their next visit (scheduled or unscheduled), regardless of further need to monitor lymphocytes on study.

Premature Study Withdrawal Visits and Unscheduled Relapse Assessment Visits were performed as necessary. All efforts were made to keep the subjects' visit schedule relative to their Baseline Visit (Day 1). All subjects who discontinued the study treatment were considered to be prematurely withdrawn from the study.

The end of study is defined as the Last Patient, Last Visit for final collection of data for the primary outcome

2.3 **MRI**

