6.4.2 Analysis Methods

In general, the covariates included in the statistical models for efficacy endpoints are selected to be consistent with analysis models in other previously reported Phase 3 MS studies. In these studies, the covariates have been demonstrated to be important factors in the analyses of the efficacy endpoints. Additionally, the statistical models and the covariates for inclusion in these statistical models for the efficacy analyses for Study 109MS303 will generally be the same as the corresponding models in Studies 109MS301 and 109MS302.

Consistent with the efficacy analysis conventions in Studies 109MS301 and 109MS302, in general, for efficacy analyses of Study 109MS303, observed data after first use of alternative MS medications in the given dataset will be excluded, or subjects will be censored at the time of first starting alternative MS medication in the given dataset if they have not experienced the event of interest. The exceptions to this are:

- Select sensitivity analyses that may be performed which consider all data regardless of alternative MS medication usage; and
- Analysis of disability progression based on EDSS, where EDSS evaluations
 performed after first use of alternative MS medication has been started will be used to
 confirm tentative progression that occurred prior to first use of alternative MS
 medication.

Alternative MS medications may include but are not limited to: interferon beta-1a, glatiramer acetate (for those subjects not receiving study-assigned GA), natalizumab, interferon beta-1b, mitoxantrone, mycophenolic acid, mycophenoloate mofetil, plasmapheresis used for the indication of MS, fingolimod, methotrexate, azathioprine,

alemetuzumab, ocrelizumab, teriflunomide, siponimod, daclizumab, cladribine, peginterferon beta-1a, cyclophosphamide, and rituximab.

Region as a covariate or in the subgroup analysis is based not only on considerations of geography but also on type of health care system and access to health care in each country. The categories for regions will be identical to those used in Studies 109MS301 and 109MS302:

- Region 1: United States (including Puerto Rico);
- Region 2: Western European countries (including Austria, Belgium, France, Germany, Greece, Ireland, Italy, Netherlands, Spain, Switzerland, and United Kingdom), plus Australia, Canada, Costa Rica, New Zealand, Israel, and South Africa; and

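### Worsening first seen shortly before a subject leaves Study 109MS303 can rarely be confirmed and is censored, which may lower the reported disability progression

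*SAP*

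**What the plan says.** **Confirmation.** Under SAP 6.4.4 the minimum EDSS increase must be "present on the next study visit occurring after 154 days or longer from the initial observation". The premature withdrawal visit may confirm under the same rule, unless it is also a relapse assessment visit.

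**Censoring.** For a subject whose last EDSS shows an unconfirmed worsening, "the censor date will be the date of the EDSS assessment prior to the last EDSS assessment". The same applies to a worsening seen "at the last EDSS assessment prior to first use of alternative MS medication that was subsequently not confirmed".

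**After a drug switch.** SAP 6.4.2 generally drops data after first use of an alternative MS medication. One exception, which opens "Analysis of disability progression based on EDSS, where EDSS evaluations", lets later EDSS scores confirm a worsening that began before the switch.

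**Leaving 303.** Protocol 11.6 states: "Subjects who receive any of these restricted medications will be required to discontinue permanently BG00012 and will be withdrawn from the study". The sentence then allows for exceptions described elsewhere in the protocol. SAP 2.2 adds: "All subjects who discontinued the study treatment were considered to be prematurely withdrawn from the study". Protocol 4.6 and 11.4 put the premature withdrawal visit, which includes EDSS, within 4 weeks of the last dose. The lymphocyte follow-up visits in Protocol 14.3.8 list no EDSS.

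**Parent studies.** Protocol 8.1 admits completers of 109MS301 and 109MS302, "including those subjects who received an open-label, approved MS therapy, and completed the modified visit schedule".

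**The concern.** The confirmation rule needs about 24 weeks of further EDSS, but a 303 subject who stops BG00012 normally has only one more EDSS, within 4 weeks. A subject who worsens and soon afterwards changes therapy therefore tends to leave the analysis as a censored observation.

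Kaplan-Meier estimation assumes that censored subjects have the same later risk as those who stay. If the worsening itself prompts the exit, that assumption fails, and it fails in the favourable direction.

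The Combined Data analysis has a second problem. Parent-phase and extension-phase events enter one curve with unequal chances of being confirmed. Long-term disability progression is a secondary objective, and these curves are its main display.

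**Working it through.** **1. The plan's own figure.** SAP 6.4.4 derives 154 days from the visit windows. With 24 weeks and a window of ±7 days at each end (Protocol 4.3): 24 × 7 − 7 − 7 = 154. It reproduces.

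**2. Who cannot be confirmed.** The last planned EDSS is 0 to 28 days after the last dose. If it takes place at 28 days, a subject whose last dose is less than 154 − 28 = 126 days after first worsening cannot be confirmed. If it takes place on the day of the last dose, the limit is 154 days. A worsening first seen at least 154 days before the withdrawal visit can be confirmed there.

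**3. Where the censor date falls** (303 EDSS intervals from Protocol 4.1 to 4.3: 24-weekly in Year 1, apart from a Week 12 assessment for some subjects; 12-weekly from Week 48 to Week 144; 24-weekly in Years 4 to 8).

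| Situation, all under 154 days from onset | Censor date |
|---|---|
| First seen at the last EDSS before an alternative drug starts | One assessment before the worsening |
| First seen at the withdrawal visit itself | One assessment before the worsening |
| First seen at a scheduled visit, raised again at the withdrawal visit, no drug started in between | The onset visit |
| First seen at a scheduled visit in the 12-weekly period, raised again 84 days later, then a drug starts | The onset visit |

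A third raised EDSS inside 154 days is possible in the 12-weekly period; the date then falls on the middle one. In no row is the event counted. Where the date moves back one scheduled interval, that is about 24 weeks in Years 4 to 8.

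**4. Effect on the curve.** Let F be the 8-year proportion if every progressor were followed to confirmation, and p the share of events lost this way, taken as constant over time. The observed hazard is (1 − p) times the true one, so the reported proportion is 1 − (1 − F)^(1 − p). The documents give neither F nor p; both are assumed here.

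| F | p = 5% | 10% | 20% | 30% |
|---|---|---|---|---|
| 15% | 14.3% | 13.6% | 12.2% | 10.8% |
| 25% | 23.9% | 22.8% | 20.6% | 18.2% |
| 35% | 33.6% | 32.1% | 29.2% | 26.0% |

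Example: 1 − 0.75^0.9 = 0.228.

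**5. Check by simulation** on the 303 EDSS schedule (assumed: 25% onset by 8 years, 50% unrelated dropout, withdrawal visit 14 days after stopping). With a mean lag of 8 weeks from onset to stopping, 4% to 9% of those who left were still confirmable; with 24 weeks, 41% to 48%. If 10% of progressors left early, the SAP rule gave 0.21 to 0.22 against about 0.23 with those leavers followed to confirmation. If 30% left early, it gave 0.17 to 0.20 against about 0.23. The comparison value is below 25% because onsets close to Week 384 or to unrelated dropout are not confirmed either.

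**6. Parent phase against extension phase.** The analysis population is subjects dosed in 303 (SAP 6.2.1). A subject rescued in a parent study therefore went on to 303 and had EDSS planned at 303 Baseline, Week 24 and Week 48 (Protocol 4.1). SAP 6.4.2 allows those scores to confirm a worsening that preceded rescue. A comparable worsening before a switch in 303 mostly has no later EDSS. This contrast exists only in the Combined Data analysis; the 303-only analysis has the loss in steps 2 to 4 but no parent-phase events.

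**The case against.** **The documents keep routes to confirmation open.** This stands in part. Confirmation at the withdrawal visit is allowed, so a reader who infers that worsening before exit can never be confirmed goes too far. The gap is limited to onset under 154 days before that visit.

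**Lymphopenic subjects are an exception.** This stands. Protocol 11.3 (Table 3) permits alternative therapy during withholding, 11.2.1 continues scheduled assessments while dosing is withheld, and SAP 6.5.6 says assessments continue off drug. One might infer that the post-switch confirmation rule can act only on parent-study data; these passages do not support that.

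**Nothing shows that worsening prompts exit.** Disability progression is not a listed withdrawal reason in Protocol 11.4, and Protocol 7.4 and 14.1 have staff act on a worsening sustained for 24 weeks. That is fair as to size. But the treating neurologist obtains or delegates the EDSS and manages routine neurological care (Protocol 14.1), so the worsening can be known before it is confirmed.

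**Unconfirmed events should not count.** True for those that would have reversed. It does not justify treating the remainder as non-informative.

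**SAP 6.4.2 already allows sensitivity analyses using all data regardless of alternative medication.** They are optional, and they cannot supply EDSS scores that were never collected.

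**The analysis is descriptive and the objective secondary.** True. This bears on priority, not on the direction of the effect.

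**Conclusion.** The point holds in a limited form. In 303, a worsening first seen less than 154 days before the premature withdrawal visit can rarely be confirmed. The rule in SAP 6.4.4 then leaves the event out and takes the subject out of the risk set, normally at or before onset. If worsening leads to switching or withdrawal, the Kaplan-Meier proportion is biased downward. The direction rests on that condition; the size cannot be calculated from the documents, and the percentages above only show scale.

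Two stronger readings are not supported:

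- That the censor date always moves back a full visit. When one later EDSS is also raised, it falls on the onset visit.
- That an apparent slowing of progression after entry to 303 is an artefact. The unequal chance of confirmation in the Combined Data curve is structural, but no counts are given, and the SAP plans proportions at key timepoints, not a comparison of rates between phases.

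**What to change.** Add to SAP 6.4.4, for both the Combined Data and the 303-only analyses:

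- **A prespecified sensitivity Kaplan-Meier analysis.** Count as an event, at onset, any worsening still present and unconfirmed at the last EDSS before alternative MS medication or premature withdrawal in 303. Exclude assessments during a relapse, following the existing 6.4.4 rule. The SAP already dates progression this way for a subject who dies of MS with a worsening in progress.
- **Its label.** Show it beside the main curve as a less favourable sensitivity estimate. It is not a strict upper bound: some counted events would have reversed, and subjects who leave before any raised EDSS is recorded are still missed.
- **Counts.** Report how many worsenings were censored this way, by treatment group and study phase.
- **A note on SAP 6.4.2.** State that the post-switch confirmation rule has little 303 data to act on.

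Reconcile SAP 6.5.6 with Protocol 14.3.8 on whether EDSS continues for lymphopenic subjects off treatment.

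The cost is a few sentences of SAP text, one additional Kaplan-Meier run per dataset and one small table. No new data are needed.
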